5.5 Study Activities

- All qualified patients will be treated with AZD7442 600 mg IM or IV at baseline.
- All qualified patients will complete a baseline Patient Experience/Clinical Outcome Assessment (COA) survey (Day 1) prior to treatment with AZD7442 600 mg IM or IV.
- All qualified patients will complete follow-up Patient Experience/COA surveys on days 2, 30, 60, 90, 120, 150, 180, 181, 210, 240, 270, 300, 330 and 360 post-baseline.

- All qualified patients will complete QoL assessment on days 2, 30, 90, 180, 270, and 360 post-baseline.
- All qualified patients will have serum concentration of AZD7442 obtained at days 30, 90, 180, 270 and 360 post-baseline.
- All qualified patients will have SARS-Cov-2 RBD-IgG antibody level obtained at baseline, days 90, 180, 270 and 360 post-baseline
- At Day 30 post-baseline, all patients will have blood obtained for T-cell assay. Measurements of CD4 T-cell and CD8 T-cell function will be performed.
- Blood will be obtained for repeat T-cell assay (CD4/CD8) at Day 210 post-baseline in a selected subset of 120 hematologic malignancy and 60 solid tumor patients.
- Repeat T-cell functional testing, SARS-CoV-2 RBD-IgG and serum concentration of AZD7442 will be performed in patients who become SARS-CoV-2 RNA by RT-PCR positive at approximately 10 days or according to study site guidelines after the patient develops a positive test.

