- In the event that a patient develops any symptoms that could be possibly related to SARS-CoV-2 infection at home or out of the office, the patient must immediately test themselves using the SARS-CoV-2 Home Test Kit that was given to them at enrollment or go to a facility that can perform an EUA approved Breath Test for SARS-CoV-2 infection.
- In the event a positive test from the SARS-CoV-2 Home Test Kit or EUA approved Breath Test for SARS-CoV-2 infection is recorded, the patient must go to a qualified testing center and receive a SARS-COV-2 RNA by RT-PCR nasal swab test. These include LabCorp or Quest Diagnostics or a location that uses one of these two labs for the analysis (e.g., CVS).
- A positive SARS-COV-2 RNA by RT-PCR test must be sent to a qualified genomics laboratory (LabCorp or Quest Diagnostics) for detailed virus analysis
- In the event that a patient tests positive for SARS-CoV-2 infection by SARS-COV-2 RNA by RT-PCR, the patient should be instructed to contact their oncology center immediately
- In the event that a patient tests positive for SARS COV-2 RNA by RT-PCR, the patient must have blood drawn for serum concentration of AZD7442, RBD-IgG antibody level and T-cell analysis in the office approximately 10

days after the patient reported a positive test or in whatever timeframe is the acceptable protocol for a positive patient returning safely to the office of the Investigator.

- In the event that a patient develops a SARS-CoV-2 infection with symptoms, the patient should be immediately treated in accordance with Investigator judgement. Such treatment should include the current standard of care for symptomatic SARS-CoV-2 positive infection depending upon availability of immediate treatment. Such patient will be followed until day 360 of the study with all study procedures and assessments.
- Automatic request for patient medical records, pharmacy fill/refill data and medical insurance claims data for all patients for the 12 months post-baseline will be sent and forwarded to MediMergent for analysis.

[figure not shown]
Schedule of Activities:

	Screening/ Day 1 Baseline	Day 2	Day 30	Day 60	Day 90	Day 120	Day 150	Day 180	Day 181	Day 210	Day 240	Day 270	Day 300	Day 330	Day 360
Visit Window (Days)		+5	± 5	± 5	± 5	± 5	± 5	± 5	± 5	± 5	± 5	± 5	± 5	± 5	± 5
Informed Consent	X														
Authorization for Release of Health Info	X														
Inclusion/ Exclusion	X														
CBC including Platelet Count (if necessary)	X														

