SARS-CoV-2 antigen test by nasal swab	X														
SARS-CoV-2 RBD- IgG Antibody level	X				X			X				X			X
T-Cell Assay			X							X					
AZD7442 Administration	X							X							
Baseline Survey	X														
QoL Surveys		X	X		X			X				X			X

Follow-up Patient Experience/COA Surveys		X	X	X	X	X	X	X	X	X	X	X	X	X	X
Serum Concentration of AZD7442			X		X			X				X			X
SARS-CoV-2 by RT-PCR if home test positive and/or symptomatic		NOTE: In the event that a patient tests positive for SARS COV-2 by RT-PCR at any time, the patient must have blood drawn for serum concentration of AZD7442, RBD-IgG antibody level and T-cell analysis in the office approximately 10 days after the patient reported a positive test or in whatever timeframe is the acceptable protocol for a positive patient returning safely to the office of the Investigator.													

10.0 Immunologic Sub-Study Activities	
10.1 Sub-Study Secretome Assay
 
IsoPlexis’ Single Cell Multiplex Secretome Assay application measures T-cell polyfunctionality (i.e., the number of cells secreting multiple cytokines). From these data, the Polyfunctional Strength Index (PSI) will be calculated as a numeric output generated as the product of T-cell polyfunctionality multiplied by the intensity of the measured signal using fluorescent imaging. These data generate functional information relating to:
 
 • CD4 T-cells (Helper T-cells) which produce cytokines to activate immune cells including B-cells, CD-8 T-cells and macrophages. • CD8 T-cells (Cytotoxic T-cells) which destroy virus-infected cells and tumor cells by either lysis and/or apoptosis. 
10.2 CD4 and CD8 T-Cell Function
 
In general, CD4 and CD8 T-cell function increases during active SARS-CoV-2 infection reflecting stimulation and activation of T-cell immune response. The magnitude of this increase in T-cell function appears to be related to the severity of COVID-19 disease. Specifically, previous data acquired in immunocompetent subjects have reported that CD4 and CD8 T-cell function significantly increase in response to active SARS-CoV-2 infection in subjects with mild-to-moderate SARS-CoV-2 disease. However, subjects with moderate or more severe SARS-CoV-2 disease may have a blunted T-cell response due to “exhaustion” of the cells’ ability to mount a sustained cellular immune response.

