17.6 Evaluations of Primary and Secondary Endpoints

The primary and secondary endpoints will be evaluated for the intent-to-treat and per protocol patient populations. The primary comparisons will be the serum concentration of AZD7442 at Days 30, 90, 180, 270 and 360 post-baseline. Serum concentration comparisons of the log-adjusted serum AZD7442 concentration will be analyzed using linear mixed models for repeated measures. Models will include disease category, overall dose, and dose/kg accounting for concomitant treatment regimen category along with appropriate treatment and time interactions. An unstructured covariance matrix will be assumed, however, in the event of non-convergence, compound symmetry, and AR (1), covariance structures will be attempted, in that order. The Least Square Means Differences, and their 95% CIs, will be reported for each timepoint (e.g., Days 30, 90, 180, 270, and 360 post-treatment).

Additional comparisons for Quality of Life (QoL) will be made between the disease category cohorts and concomitant treatment regimen categories. The disease category cohorts are solid tumor cancers and hematologic cancers. Concomitant treatment regimen categories will be defined as chemotherapy only, immunotherapy

only, targeted therapy only, other therapy/ combination therapy only. Differences in the primary endpoints will be assessed using a two-sided statistical significance level of 0.01, adjusting for planned multiple comparisons. All other differences will be assessed using a two-sided statistical significance level of 0.05.

The secondary endpoint comparisons will be made:

- between concomitant treatment regimen categories and
- between disease category cohorts

The between concomitant treatment regimen categories will account for the between disease category analyses. These secondary endpoint comparisons will be made using a logistic regression or linear mixed model accounting for potential patient and disease factors where appropriate. Additional secondary endpoints are as noted previously. The secondary endpoints will be analyzed for the Intent-To-Treat (ITT) population with a Per-Protocol (PP) sensitivity analysis.

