17.8 Immunologic Sub-Study

In the immunologic sub-study, pre-specified analyses will evaluate CD4 T-cell and CD8 T-cell data including Polyfunctional Strength Index at Day 30 post-baseline in all 1,500 cancer patients and then compare these results against similar T-cell data for any patient who tests SARS-COV-2 RNA by RT-PCR positive at any timepoint post-baseline. In addition, results will be compared to prior data for these tests obtained from normal healthy donor subjects.

Relationships between AZD7442 serum concentration, RBD-IgG antibody level and T-cell function will be assessed as described in Section 10.2

Lab data will be extracted from the nearest time point to the blood draw associated with T-cell assay testing . An unpaired Wilcoxon-test will be used to determine the statistical difference between (1) WOS \leq 2 and WOS = 3-4 and (2) WOS = 3-4 and WOS = 5-8 and (3) WOS \leq 2 and WOS \geq 3. Spearman correlation coefficient will be

calculated to observe the associations between clinical data and WOS disease severity. In the current study, baseline T-cell polyfunctionality and PSI will be determined at two timepoints in immuno-compromised cancer patients: 30-days after initial administration of AZD7442 and in temporal proximity to the time that a patient has confirmed SARS-CoV-2 by RT-PCR evidence of SARS-CoV-2 infection.

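### The day of the post-infection T-cell draw is uncontrolled and probably related to severity, so the unadjusted Wilcoxon comparisons of WOS groups in Section 17.8 cannot separate severity from time since infection

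*Protocol*

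**What the plan says.** **Timing of the draw.** Section 5.5 calls for repeat T-cell testing "at approximately 10 days or according to study site guidelines after the patient develops a positive test". Section 9.3 gives about 10 days, or "in whatever timeframe is the acceptable protocol for a positive patient returning safely to the office of the Investigator", and the note in the Schedule of Activities says the same. Section 9.3 and the note place the draw in the office. Scheduled T-cell draws have a window of ±5 days (Section 9.3); this one has none.

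**Analysis.** Section 17.8 states: "An unpaired Wilcoxon-test will be used to determine the statistical difference between" three pairs of WOS groups (≤2 and 3-4; 3-4 and 5-8; ≤2 and ≥3). It gives no covariate or time term, and the sentence does not name the response variable. Sections 4.1 and 16.1 relate change from Day 30 in T-cell function to WOS. On the error level, Section 17.6 says "All other differences will be assessed using a two-sided statistical significance level of 0.05".

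**Severity grade.** In Section 11.1, WOS 3-7 all mean hospitalized and 8 is death. Section 20.1 has the Clinical Events Committee assign the WOS that belongs to the time of the T-cell draw. Section 14.3 lists the highest WHO severity class as an outcome. Section 17.8 does not say which one forms its groups.

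**Expected pattern.** Section 10.2 says "In general, CD4 and CD8 T-cell function increases during active SARS-CoV-2 infection" and that "subjects with moderate or more severe SARS-CoV-2 disease may have a blunted T-cell response due to" exhaustion of the cells.

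**The concern.** By the protocol's own account, T-cell function changes with active infection, so a measured value depends on when the blood was taken. The draw day is open-ended, and the release condition is that a positive patient may safely come back to the office. A patient still in hospital cannot give an office sample, so patients who reach WOS 3 or above will probably be sampled later than those who stay at home.

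An unadjusted two-group rank test then compares groups that may differ in both severity and time since infection. Whether a difference reflects one or the other cannot be read from the result. At stake is the sub-study's description of T-cell response by COVID-19 severity. A lower value in sicker patients would match the blunting that Section 10.2 already describes, so a timing artefact in that direction would be easy to accept as biology.

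**Working it through.** The protocol gives no power, group size or error rate for this comparison, so there is no stated figure to reproduce. The check has two parts.

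**1. What happens under each severity grade**

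- *Highest WOS of the episode (Section 14.3).* Formerly hospitalized patients stay in the WOS ≥3 groups and are probably drawn later. If function falls after the acute phase, their values are lower for reasons of timing alone.
- *WOS at the draw (Section 20.1).* A discharged patient sampled in the office is no longer hospitalized, so cannot be WOS 3-7 and is classed as ≤2. WOS 8 cannot be sampled. The 3-4 and 5-8 groups nearly empty. Late-drawn, formerly severe patients lower the WOS ≤2 group if function declines, which works against the blunted pattern.

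The two grades give different failures from the same cause, an uncontrolled draw day.

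**2. Illustrative size under the highest-WOS reading**

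None of the inputs below is in the protocol except the two-sided 0.05 level and the 10-day default. There is no true severity effect:

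- Log T-cell measure: y = −k·t + e, with k = ln 2 / half-life and e normal with SD 0.8.
- Draw day t: mean 10, SD 3 in the milder group; mean 10 + d, SD 6 in the more severe group (SD 3 when d = 0); none before day 5.
- Two-sided Wilcoxon (Mann-Whitney) test, 2,000 runs per cell. Monte Carlo standard error near 5%: √(0.05 × 0.95 / 2000) ≈ 0.005.

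The spurious mean shift is ln 2 × d / half-life. For d = 10 days:

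- half-life 30: 0.693 × 10/30 = 0.231, or 0.231/0.8 = 0.29 residual SD
- half-life 14: 0.693 × 10/14 = 0.495, or 0.62 residual SD
- half-life 7: 0.693 × 10/7 = 0.990, or 1.24 residual SD

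False-positive rate of the unadjusted test:

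| Patients | Extra delay d | No decline | 30 days | 14 days | 7 days |
|---|---|---|---|---|---|
| 60 vs 15 | 0 | 0.046 | 0.050 | 0.051 | 0.046 |
| 60 vs 15 | 5 | 0.041 | 0.080 | 0.173 | 0.454 |
| 60 vs 15 | 10 | 0.048 | 0.151 | 0.499 | 0.928 |
| 60 vs 15 | 20 | 0.055 | 0.481 | 0.971 | 1.000 |
| 120 vs 30 | 5 | 0.059 | 0.102 | 0.289 | 0.715 |
| 120 vs 30 | 10 | 0.036 | 0.275 | 0.787 | 0.995 |
| 120 vs 30 | 20 | 0.042 | 0.781 | 1.000 | 1.000 |

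Nearly all excess rejections show lower function in the more severe group. With 60 vs 15, d = 10 and a 14-day half-life, 0.498 of the 0.499 do. A linear model on the log scale with draw day as covariate gave 0.042 to 0.058 in every cell. It was fitted with the correct form of decline and overlapping draw days.

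**Where adjustment stops helping.** If mild cases were all drawn on days 8-14 and hospitalized cases on days 20-40, adjustment would rest on extrapolation. A restriction to days 7-21 would keep 2 of the 21 severe days. If draws are spread evenly, that leaves 12 × 2/21 ≈ 1 of 12 severe patients, or 40 × 2/21 ≈ 4 of 40.

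**The case against.** The strongest reply has four parts.

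- *The protocol does not say that sicker patients are drawn later.* The default is about 10 days for everyone, Section 17.8 describes the sample as close in time to RT-PCR confirmation, and site return rules can delay mild cases too. This stands: the link with severity is an inference from the office venue and the hospital-based definition of WOS 3-7.
- *No decline is documented.* Section 10.2 describes a rise during infection and gives no rate of fall. This stands: with no decline the false-positive rate stays at about 5% whatever the delay.
- *Section 17.8 attaches no interpretation to the test.* Blunting appears in Section 10.2, worded as a possibility, and the interpretation table announced there is not legible in the text at hand. This stands. A reader might infer that the sub-study will report delay as exhaustion; the documents do not go that far.
- *Covariates for a sub-study comparison are commonly left to the SAP, and Section 17.10 makes the breakthrough analysis descriptive.* This stands only in part. Section 17.8 names the test and its groups, so the method is fixed here. The covariate provisions in Sections 17.6 and 17.11 concern logistic and linear models, not a two-group rank test.

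A reader might also infer that the bias takes the same form whichever WOS is used. It does not: under WOS at the draw, the groups are emptied and the direction may reverse.

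**Conclusion.** The point holds in a limited form. Draw day is uncontrolled and probably related to severity, and the planned test cannot separate severity from time since infection under either reading of WOS. The protocol also leaves the reference time of WOS unreconciled between Sections 14.3, 17.8 and 20.1.

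The size is conditional. Under the highest-WOS reading, the illustrative false-positive rate runs from about 5% (no decline or no extra delay), through 8% (5 days, 30-day half-life, 60 vs 15), to well above 50% with rapid decline and long delay. These rates rest on assumed delay, decline, SD and group sizes, and they illustrate the risk without predicting this trial's error rate. The documents do not support a claim that later sampling of sicker patients is designed in, or that a false finding of exhaustion is expected.

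The wording should be changed. The primary endpoint is unaffected, and no trial decision is stated to depend on this comparison.

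**What to change.** In Section 17.8:

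1. State that the severity groups use the highest WOS of the episode, or otherwise reconcile Sections 14.3, 17.8 and 20.1 and name one reference time.
2. Name the response (T-cell measure as change from Day 30). Make the main comparison a rank-based or log-scale regression of it on WOS group, adjusted for days from first positive RT-PCR to the draw.
3. Add a sensitivity analysis limited to draws in one common interval, fixed in advance (for example 7 to 21 days after the positive test).
4. Report adjustment for corticosteroid or other COVID-19 treatment only as a further sensitivity analysis. Such treatment is given partly because of severity, so adjusting for it in the main model could remove part of the effect under study.
5. Keep the unadjusted Wilcoxon tests as descriptive, and tabulate draw day by WOS group.

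The cost is analysis wording. Test and draw dates, and treatment records, come from data the trial already obtains. The downsides are that adjustment is informative only where draw days overlap between groups, and that the restricted analysis loses patients, possibly most of the severe ones. If the table of draw days shows little overlap, the comparison should be reported as unable to separate severity from timing.

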
Clinical Hypotheses to be Evaluated
	
The primary clinical hypothesis to be evaluated is that in patients treated for either solid tumor or hematologic malignancy cancer, a dose of AZD7442 600 mg IM or IV every 6 months will prevent symptomatic SARS-CoV-2 infection including SARS-CoV-2 related hospitalization and/or SARS-CoV-2 related death, independent of type of cancer therapy up to 12 months post-dose. The possibility of a break-through SARS-CoV-2 infection may be influenced by type of cancer, current cancer treatment or length of time post-baseline administration of AZD7442.
 
2.2 Serum Concentrations of AZD7442
 
We hypothesize that serum concentrations of AZD7442 will not be different between solid tumor or hematologic malignancy treatment regimens at any time point post-baseline. We believe that serum concentration of AZD7442 may be correlated with IgG antibody level to SARS-CoV-2 and CD4/CD8 level as a measurement of T-Cell function as well as symptomatic SARS-CoV-2 infection, including SARS-CoV-2 related hospitalization and/or SARS-CoV-2 related death. We also expect to find that AZD7442 side-effects will not be significantly different between the four strata of cancer therapy (chemotherapy only, immunotherapy only, targeted therapy only, other therapy/combination therapy only).
 
2.3 T-Cell Function
 
We hypothesize that T-cell function obtained at Day 30 post AZD7442 administration in cancer patients will be within the normal range compared to historical healthy control patients' CD4/CD8 data. In addition, we hypothesize that patients who experience breakthrough SARS-CoV-2 infection will have an increase in T-cell function compared to data acquired on Day 30 post AZD7442 administration and that this increase will be in the range of expected results in historical control patients.

3.0 Study Objectives
	
3.1 Primary Objective:
 
The primary objective is to quantify the serum concentration of AZD7442 at 1,3, 6, 9 or 12-months post-baseline in all qualified cancer patients treated with AZD7442 600 mg IM or IV every 6 months.
 
3.2 Secondary Objectives:
 
The secondary objectives of the study are as follows:

- Compare the incidence of symptomatic SARS-CoV-2 infection including SARS-CoV-2 related hospitalization and/or SARS-CoV-2 related death between solid tumor and hematologic malignancy patients.

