
15.0 Interim Analysis
	
the analysis will determine which group is more likely to experience such infections.
 
An interim analysis will be performed after the first 6-month assessments are completed for the first 50% of the targeted patient sample for each malignancy, i.e., 750 patients including 600 solid tumor and 150 hematologic malignancies. The primary endpoint of the interim analysis will be the serum concentration of AZD7442 for all patients with comparisons between disease categories.
 
Secondary analyses will be conducted on the following measures in all patients included in the interim analysis set:
 
 • Incidence of break-through infections in all patients and then sub-divided into solid tumor and hematologic malignancy. • Time to infection compared between solid tumor and hematologic malignancy • RBD-IgG levels for all patients with comparisons between disease category • CD4/CD8 levels for all patients with comparisons between disease category

16.0 Immunological Sub-Study Endpoints
	
16.1 Immunologic Sub-Study Endpoints
 
 • Comparison of CD4 T-cell and CD8 T-cell function in all cancer patients at 30 days post initial administration of AZD7442 to similar tests performed in normal healthy donor subjects • Comparison of the relationship between different cancer treatment regimens and T-cell function in all cancer patients at 30 days post administration of AZD7442 • Comparison of the relationship between type of cancer (solid vs. hematologic) and T-cell function in all patients at 30 days post administration of AZD7442 • Comparison of the immunologic profile relating to AZD7442 serum level and T-cell function at the time of PCR positive SARS-CoV-2 infection in all cancer patients to Day 30 T-cell functionality • Comparison of the relationship between change from Day 30 in AZD7442 serum level, T- cell function and World Health Organization Ordinal Scale

	
(WOS) for SARS-CoV-2 disease severity in all cancer patients with documented PCR positive SARS-CoV-2 infection
 
 • Comparison of the relationship between change from Day 30 in AZD7442 serum level, T- cell function and World Health Organization Ordinal Scale (WOS) for SARS-CoV-2 disease severity in all cancer patients with documented RT-PCR positive SARS-CoV-2 infection based on type of cancer treatment.

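### The T-cell response to breakthrough infection is judged against Day 30 with no uninfected trial patients followed over time, and the Day 210 repeat assay that could supply them appears in no stated analysis

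*Protocol*

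**What the plan says.** Protocol 2.3 hypothesises that "patients who experience breakthrough SARS-CoV-2 infection will have an increase in T-cell function compared to data acquired on Day 30", and that "this increase will be in the range of expected results in historical control patients". Section 10.2 supplies the reading of such a rise: in general, "CD4 and CD8 T-cell function increases during active SARS-CoV-2 infection reflecting stimulation and activation of T-cell immune response". Section 16.1 makes it a sub-study endpoint, comparing AZD7442 level and "T-cell function at the time of PCR positive SARS-CoV-2 infection in all cancer patients to Day 30 T-cell functionality".

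Section 17.8 sets Day 30 results in all 1,500 patients against results from anyone who turns RT-PCR positive at any later time. It then states that T-cell polyfunctionality and the Polyfunctional Strength Index "will be determined at two timepoints in immuno-compromised cancer patients: 30-days after initial administration of AZD7442" and close to confirmed infection. The other comparators in 17.8 are healthy donors and WHO severity groups.

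Section 5.5 nevertheless schedules a third occasion: "Blood will be obtained for repeat T-cell assay (CD4/CD8) at Day 210 post-baseline in a selected subset of 120 hematologic malignancy" patients and 60 solid tumor patients. Section 9.3 repeats this, and the Schedule of Activities marks a T-cell assay at Day 210.

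**The concern.** A before-and-after difference in infected patients alone mixes two things: the response to infection and whatever would have happened anyway since Day 30. The protocol itself gives reasons to expect the second. Cancer treatment is examined as a correlate of T-cell function (4.1) and may end or change during follow-up. Extra vaccine doses are allowed from 14 days after dosing (5.4). Clinical stability is reassessed at months 3 and 6 (5.2).

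If T-cell function tends to recover over the year, a rise could be credited to infection when infection did nothing. If it tends to fall, a real response could be hidden. The sub-study was designed to learn whether these patients mount a T-cell response, so this ambiguity bears on its main message.

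**Working it through.** **1. Where Day 210 appears.** The protocol states no power, effect size or sample size for the T-cell comparison, so there is no figure to reproduce. Tracing each mention:

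- Collected: 5.5, 8.1, 9.3, Schedule of Activities. The subset is 120 + 60 = 180 patients, which is 12% of 1,500, 40% of 300 hematologic and 5% of 1,200 solid.
- Sub-study objectives (4.1): Day 30 and time of infection only.
- Sub-study endpoints (16.1): Day 30 and time of infection only.
- Interim analysis (15.1): CD4/CD8 by disease category, with no Day 210 analysis.
- Analyses (17.8 to 17.10): Day 210 is not named.
- Per-Protocol definition (17.4): completing Day 210 is a membership criterion.

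**2. Why the comparison cannot separate the two effects.** For a patient sampled s days after Day 30, expected change = drift(s) + infection effect, with s up to about 360 − 30 = 330 days. Day 30 values in all patients say nothing about drift(s). Healthy or historical controls are a different population. Severity groups among the infected all carry the drift. Only the Day 210 subset informs drift in trial patients, at s = 180.

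**3. Illustration of size.** Everything here is assumed: 30, 75 or 150 infected (2%, 5%, 10% of 1,500), no infection effect, two-sided 5% (the level 17.6 sets for non-primary comparisons), and a paired test that the protocol does not name.

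*Closed form.* With a drift of d SDs of within-patient change, the chance of a significant rise is P(T > t[0.975, m−1]), where T is noncentral t with m−1 degrees of freedom and noncentrality d√m (nominal 2.5%):

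| Infected m | d = 0.1 | d = 0.2 | d = 0.3 |
|---|---|---|---|
| 30 | 8% | 18% | 36% |
| 75 | 14% | 40% | 73% |
| 150 | 23% | 68% | 96% |

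*Simulation.* Sample day was uniform over 40 to 370, drift was linear and reached 0.1, 0.2 or 0.3 SD by Day 210, and within-patient correlation was 0.5 (SD of change √(2 × 0.5) = 1). A signed-rank test on 75 infected patients was significant in 14%, 37% and 68% of trials. At 0.2 SD it was 16% with 30 infected and 64% with 150. At correlation 0.7 with 75 infected the three rates were 18%, 54% and 86%. With zero drift there is no inflation.

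**4. What a Day 210 contrast costs.** Take infected patients in the trial's 20:80 hematologic-to-solid mix and adjust for disease category. In units of the SD of change, the information on the infection effect is the sum over categories of n(inf) × n(ctl) / (n(inf) + n(ctl)):

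- m = 30: 6×120/126 + 24×60/84 = 5.71 + 17.14 = 22.86. SE ratio to the uncontrolled change: √(30/22.86) = 1.15.
- m = 75: 15×120/135 + 60×60/120 = 13.33 + 30 = 43.33. Ratio √(75/43.33) = 1.32.
- m = 150: 30×120/150 + 120×60/180 = 24 + 40 = 64. Ratio √(150/64) = 1.53.

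If both groups share the same linear drift, the contrast's error rate stays at about the nominal 5% (4–6% in the simulation).

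**5. Where the contrast itself fails.** Suppose the subset shifts by 0.2 SD (through selection or the repeat dose) and infected patients do not drift. With m = 75, SE = 1/√43.33 = 0.152, and 0.2/0.152 = 1.32. The contrast then rejects falsely in about P(Z > 1.96 − 1.32) = 26% of trials (about 10% at 0.1 SD, 51% at 0.3 SD), while the uncontrolled test stays near 5%. Also, all controls sit within 5 days of Day 210. An elapsed-time slope would thus come almost wholly from infected patients, and the contrast speaks mainly to infection around Day 210.

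**The case against.** The strongest reply has four parts.

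- **The model is open.** For Day 30 versus infection, 17.8 names no test, pairing or covariates; its unpaired Wilcoxon and Spearman methods concern WHO severity. Section 17.12 leaves other endpoints to case-by-case models, including repeated-measures models, and an analysis plan may exist. This stands against any claim that the protocol prescribes a failing test. It does not answer the main point: 17.8 positively fixes two timepoints and leaves out a scheduled one, and 17.12 names no Day 210 analysis.
- **Breakthrough cases already get a descriptive analysis (17.10).** True, but that section supplies no comparator, and 2.3 and 16.1 still pose the rise from Day 30 as a hypothesis and an endpoint.
- **The interpretation table announced in 10.2 is not visible in the copy reviewed.** How individual rises are read therefore cannot be fully checked, and nothing here rests on that table.
- **Day 210 is an imperfect control.** It is a single timepoint, 30 days after the Day 180 dose, in a subset with no stated selection rule and a 2:1 hematologic mix against the trial's 1:4. This stands in full, and step 5 shows the harm it could do.

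A reader might infer that the trial will probably report a false T-cell response, that the Day 210 data will go to waste, or that the contrast should replace the within-patient change as the test. The documents support none of these. They give no drift, infection count or paired test. A protocol without its analysis plan cannot show that data will never be analysed. The contrast exchanges one untested assumption for another.

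**Conclusion.** The point holds in this form. As written, 2.3, 16.1 and 17.8 give an uncontrolled before-and-after comparison over up to 11 months, so a change from Day 30 cannot be attributed to infection. The two timepoints in 17.8 contradict the Day 210 assay in 5.5, 9.3 and the Schedule of Activities. No stated objective, endpoint or analysis uses that assay.

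The textual findings need no assumptions. The error rates in step 3 do: they show how a modest shared drift could mislead a paired test and are not estimates for this trial. The consequence is confined to the immunologic sub-study; the primary serum-concentration analysis is untouched. It is worth correcting because the interpretation of a stated hypothesis depends on it and the samples are already scheduled.

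**What to change.** - Add Day 210 to the timepoints in 16.1 and 17.8, and state its purpose and how the 180 patients are selected. Align 5.6 and 8.1, which imply a second T-cell sample for every patient, with the subset in 5.5 and 9.3.
- Pre-specify in 17.8 a contrast of change from own Day 30: the post-infection sample in RT-PCR-positive patients against the Day 210 sample in subset patients not infected by Day 210. Use a linear model with terms for infection, elapsed time since Day 30 and disease category.
- Report this beside the within-patient change in infected patients, and say that a rise will not be attributed to infection on the uncontrolled change alone.
- State the limits: roughly linear drift; the same drift assumed in subset and infected patients, open to bias from selection and from sampling 30 days after the Day 180 dose; and a single control timepoint.

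The cost is wording and one added model, with no extra blood draws. The contrast is less precise than the uncontrolled change, with a standard error about 1.1, 1.3 and 1.5 times as large for 30, 75 and 150 infections.
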